1. STUDY OBJECTIVES/HYPOTHESIS

Primary Objective(s)

Primary aim: Compare the diagnostic yield of Magnetic Resonance Enterography (MRE) with Small-Bowel Capsule Endoscopy (SBCE) in pediatric patients with known

Inflammatory Bowel Disease (IBD) including Crohn's disease (CD) or indeterminate colitis (IC).

Secondary Objective(s)

1. To determine the detection rate of small bowel disease / complications, subjected to a strategy of Wireless Capsule Endoscopy (WCE) – small bowel screening / surveillance vs MRE in a pediatric tertiary medical institution.
2. Compare sensitivity and specificity of both MRE and WCE in identifying patients with active vs. inactive CD and IC as defined by the Pediatric Crohn's disease activity index.
3. To correlate the findings detected on WCE by Lewis score with Crohn's disease activity index.

2. BACKGROUND

Crohn's Disease CD represents a chronic idiopathic disorder primarily involving the gastrointestinal tract. Although any part of the gastrointestinal tract can be involved, the most common pattern in paediatric patients is ileocecal involvement. More proximal small intestinal involvement is more common in pediatric patients with a prevalence of up to 20%[1]. The clinical presentation and sequelae of small intestinal involvement in Crohn's Disease is varied and include nutritional sequelae resulting in growth delay and including iron deficiency anemia, stricture formation, obscure abdominal pain and eventually obstruction[1,2]. Small intestinal screening in suspected Crohn's Disease and periodic small intestinal surveillance in known cases is the current accepted standard of care [1]. There are several modalities that can be employed toward visualizing the small intestine although there is no gold standard[1]. Options include contrast studies including small bowel series and computed tomography enterography (CTE). Gadolinium enhanced MRI imaging (GAD MRI) of the abdomen and small bowel enema are technically more demanding but may be more sensitive in early disease.

There is growing concern with recurrent radiation exposure particularly from routine radiologic modalities in children [3], this is especially relevant in pediatric Crohn's Disease in so far as CT enterocolysis abdomen and small bowel series are often seen as complementary [3]. Although small bowel series is accepted as a routine diagnostic modality in pediatric IBD if fluoroscopy time is kept to a minimum, its limitations are well defined and are especially relevant in the early stages of IBD wherein fistulising, stricturing disease is less common. Magnetic resonance enterography (MRE) has a diagnostic effectiveness comparable to other radiological modalities for evaluation of adult patients with CD, [1,2]but without radiation exposure. However it is limited by expense, the availability of the requisite equipment and software, need for sedation in pediatric population, limited expertise in accurate interpretation especially in early lesions such as are more common in pediatric IBD, and overall insensitivity to early mucosal lesions including vascular abnormalities.

Alternative modalities for small bowel imaging are being studied and include the routine use of wireless-video capsule endoscopy (WCE) which allows visualization of the small-bowel mucosal lesions in Crohn's disease [4]. Because the risk for capsule retention in suspected or established Crohn's disease is significantly increased; in some series up to 13%; pre WCE small bowel imaging or patency capsule has become standard of care.

The main indications for WCE in Crohn's disease are to establish the diagnosis, to assess disease prognosis, disease activity, and mucosal healing post therapy, and to define the extent and severity of disease [5]. A small, prospective study of 27 patients suspected to have Crohn's disease, revealed a sensitivity of 93% and specificity of 84% for the WCE examination compared to surgical and enteroscopic tissue samples, and demonstrated a significant change in their management [6]. Another prospective randomized blinded study adults (N = 21) reported the sensitivity and specificity of CD in terminal ileum were 100% and 91% by WCE[7]. Jensen suggested WCE as first line modality for detection of small bowel CD beyond the reach of colonoscopy [7]. In adults with known CD, Karoui et al evaluated WCE in a prospective study (N = 20) comparing it to radiological techniques and concluded that WCE is more accurate in detection of small bowel lesions in CD[8].

In a small retrospective study (N=7), most older children and adolescents with unexplained growth failure and normal small bowel series were found to have Crohn's disease involving the small intestine [9]. A recent prospective study performed in 60 pediatric patients with suspected Crohn's disease showed both MRE and WCE appeared complementary methods for the detection of Crohn's disease in suspected CD patients. Both have a high degree of accuracy, sensitivity, and specificity at 98.3%, 100%, 97.6%, and 91.9%, 90.9%, 92.3%, respectively [10]. Another large prospective study in children (N=117) with established or suspected CD demonstrate a statically significant diagnostic yield of WCE in reclassifying indeterminate colitis IC into CD (60%), detection of CD lesions in known CD (41%) and establishing new diagnosis in suspected CD(50%) compared to other radiological modalities[11].

Overall tolerance and safety: WCE is safe in children approximately 9 years of age and older, endoscopic placement is feasible in individuals refusing or unable to swallow the capsule but adds to the potential morbidity and expense of the procedure. WCE has been safely performed in children as small as 11.5 kg [4]. Jensen and colleagues studied the factors associated with incomplete WCE studies and their diagnostic yield in pediatric patients. In this study, 22% of the WCE studies were incomplete, and in 12 (44%) of these were normal pre-WCE radiologic findings [4].

WCE should be used with caution and most likely contraindicated in patients with known swallowing disorders, gastrointestinal obstruction and fistulas. The risk for WCE retention (which is defined as capsule remains in digestive tract for a minimum of 2 weeks or it requires direct intervention to aid in its passage) in Crohn's disease patients is estimated to be 5%–13% [12]. Even though Crohn's disease is reported to have the most

common retention rate it is reported in metanalysis that retention rate is 2.6% in all prospective and retrospective studies [13].

Atay and colleagues investigated the risk factors for capsule retention in their cohort (n = 207) of pediatric patients studied by WCE[14]. Capsule retention complicated 1.4% of studies; all in known Crohn's patients. The risk in known CD patients was therefore 5.2%, and rose to 37% if there had been a prior small bowel series showing small bowel disease, and to 43% if the patient's body mass index was less than the 5th percentile, presumably indicative of more severe, longstanding small bowel involvement [14].

The Patency Capsule (Agile ®) was developed, tested, and shown to greatly curtail the possibility of small bowel capsule retention and therefore obviate the need for surgery[15]. A pre-WCE, patency capsule (PC) strategy has completely removed the incidence of capsule retention[15]. The caveat to PC testing is that it also impacts the utility of WCE overall in so far as a proportion of patients cannot thus be studied (failed PC passage). The Patency capsule is identical in shape and size to the actual WCE device but in the presence of small intestinal enzymes it will dissolve starting at 30 hours post ingestion, thus slow passage or retention of PC in the small bowel signals a risk of capsule retention and are usually interpreted as a contraindication for WCE.[16]

The safety of PC was evaluated in a multicenter clinical trial (N=106) with known Crohn's disease and intestinal strictures which showed that all cases had a complete passage of WCE if patency capsule proved patency[15]. Adverse events of PC were reported in 17/106 patients such as abdominal pain was managed with conservative management. One case developed obstruction and underwent surgery which seems unrelated to the patency capsule because it was not retained at the time of surgery (1/106) [15]. Another retrospective study by Cohen showed that after successful passage of the patency capsule in 19 patients, who proceed to have WCE after one week with one patient experiencing capsule retention[17]. The results of the study led to the diagnosis of CD and the patient subsequently underwent a needed ileocecal resection [17].

RATIONALE

Most of the studies evaluating the roles of MRE and WCE conducted in pediatric patients have been retrospective with the main goal of making a diagnosis in patients with suspected IBD. The current study is the first prospective study in children with known IBD assessing the roles of MRE and WCE in identifying disease exacerbation. This study will help to identify if capsule endoscopy is superior or complementary to MRE in the evaluation of suspected disease exacerbation in IBD patients.

3. STUDY DESIGN

- Prospective single blinded comparison of a cohort of pediatric patients with indeterminate colitis (IC) or Crohn's disease (CD) who are scheduled to undergo

routine small bowel screening or surveillance using MRE. Subjects will swallow a patency capsule (PC) to study bowel patency. If MRE shows stenosis or stricture subject and caregivers will be given the opportunity to continue with the study or withdraw. Those patients, who pass an intact PC, usually within 40 hours, will ingest the wireless capsule endoscopy (WCE). The WCE will be performed within 1 week of completion of MRE. Both modalities diagnostic yields will be compared to detect Crohn's disease lesions/complications and correlate the findings with Pediatric Crohn's Disease Activity Index (CDAI).

4. TARGET STUDY POPULATION SPECIFICS

Study participants (n=50) ages 4 – 17.99 years of age will be recruited for this study. Patients will be identified for recruitment after an initial evaluation in gastroenterology clinic at Children's Mercy (CM), if they are diagnosed with IBD and planned to have MRE as part of standard of care for clinical indication to evaluate small bowel disease.

Inclusion Criteria:

- Patients aged 4 to 17.99 years at time of investigation
- IBD/CD and IBD/IC diagnosed based on standard clinical – histologic criteria
- Patient is scheduled to have MRE as standard of care for evaluation of disease severity/ complication.
- Signed permission/assent/consent

Exclusion Criteria:

- IBD diagnosis not established
- Recent intestinal tract surgery / resection involving small bowel
- Use of NSAIDs 4 weeks prior to the Capsule endoscopy study.
- Patients are on prokinetic medication.
- Swallowing disorders, esophageal stricture or patients unable to swallow the capsule.
- Presence of gastrointestinal obstruction or ileus.
- Patient with implanted electro-medical device or pacemakers.

5. STUDY PROCEDURES

- Prior to MRE visit:
 - The provider ordering the MRE will contact a member of the study team to let them know an MRE for a patient has been scheduled.
 - Team members will have the option of calling the parent/authorized representative of the family to ask if they would like to hear about the study. If yes, the team member will explain the study and follow protocol for telephone consent or agree to meet with the family when the patient comes in for his/her MRE.

- Standard of Care MRE visit:
 - At the MRE procedure visit, if not previously consented, the subject and family will be approached by a member of the study team to explain the study and ask if they would like to participate. If a subject is unable to stay after MRE to complete patency capsule procedures, the family can choose to return in the next 1-2 days to any CMH GI location with study staff to complete the procedure.
- Post Consent:
 - Subject will have lab draw for: Hemoglobin/Hematocrit (Hgb/Hct), erythrocyte sedimentation rate (ESR), Albumin.
 - Lab draw at time of standard of care IV placement for MRE if possible
 - If not possible to complete at MRE subject may have at the time of patency capsule or WCE visit.
 - If the subject has had these labs drawn for standard of care in the last 2 weeks, those values will be used in place of this lab draw
 - Patency capsule (performed as a part of the research study): A dissolvable capsule the same size as the PillCam SB capsule, with a radio frequency identification (RFID) tag (size 3mm x 13mm) packed in a lactose and barium powder. If the capsule is retained more than 80 hours it will dissolve into small pieces that can pass naturally through the GI tract after 2-5 days. Due to its ability to dissolve it is unlikely that if the capsule is retained that it will cause any further complications.
 - Subject will swallow the capsule. They will then follow the below schedule.
 - 0-2 hours nothing to eat or drink
 - 2-4 hours clear liquid only
 - 4+ hours may eat and drink freely
 - Miralax dose at the time the child can eat: Less than 5 years of age 2 doses (34 grams), 5-10 years of age 3 doses (51 grams), greater than 10 years of age 4 doses (68 grams).
 - *Due to the age range of subjects in the study they will likely be in school during the time they are enrolled in the study. To allow for greater flexibility for families. The patency capsule can be swallowed at home or*

with a parent/caregiver at school during the lunch period. The patient or caregiver must record the exact time the pill is swallowed to calculate

time till x-ray. This will allow for the subsequent miralax dose and any necessary x-rays to take place after school hours.

- Subjects should not be around electromagnetic fields while PC procedure is performed
- Subject will receive Miralax and instructions for WCE home prep.
- Post Patency Capsule Swallow
 - A follow up phone call will take place with the subject and family the day following patency capsule ingestion. Subjects will return to CM radiology for an abdominal x-ray within 28-40 hours, as close as possible to 30 hours after swallowing the patency capsule unless they report to the study team that they visibly saw the excreted capsule. If the patency capsule has passed through the bowel then the subject will continue with WCE procedures.
 - *The study doctor or the subjects regular GI doctor or an appropriate delegate will discuss the results of MRE and patency capsule with the subject and guardian to decide if is a possible increased risk of retention and families will be able to decide if they would like to continue with study procedures. GI providers will be added to the MARS electronic IRB submission form and listed as study staff when they refer a subject so they are identified as being able to participate in these study procedures.*
- WCE Visit
 - The subject will return to the GI clinic to complete the WCE 5 days (\pm 2 days) from the time of patency capsule ingestion. Subject dietary restrictions the day before the wireless capsule endoscopy (WCE) visit.
 - To allow for greater flexibility for those subjects who are in school at the time of study procedures. The miralax prep may be started after school however the no solid foods after noon must still be observed.
 - Subject will fast for 8 hours overnight.
 - WCE visit (approximately 1 hour) - performed as a part of the research study.
 - The WCE used in this study is the PillCam SB video capsule (Given Imaging, Israel) that measures 11mm \times 26mm and weighs less than 4 g.
 - Subjects will wear a belt sensor around their waist and a recording device attached to it for the duration of the WCE study. device

- Subject will be asked questions about any symptoms and/or new medications.
- Subject will swallow the capsule in GI procedure room.
- Subjects should not be around electromagnetic fields while WCE procedure is performed
- Subject may drink clear liquids 3 hours after ingesting the capsule
- Subject may eat solid foods 6 hours after ingesting the capsule, respectively.
- Subjects will be asked to return to the GI procedure room to return the belt sensor 8-12 hours after ingesting the WCE

At times due to Crohn's disease a portion of the bowel can become inflamed and narrowed. These stenosed/strictured areas are not often easily identified until a patient has symptoms of bowel obstruction. It is possible that the capsule may identify these areas because it is not able to pass through the decreased space in the lumen. If the family or subject does not visually see the capsule pass within 2 weeks from the time of capsule ingestion, then an x-ray will be performed to assess if it is retained in the bowel. If the capsule is retained, the PI or Sub-I will notify the subject's primary GI physician about the finding and medical management will be attempted to reduce the subject's inflammation so that the capsule may pass through. In some cases the capsule may identify such a diseased portion of the bowel that it needs to be surgically removed. This capsule retention due to a strictured portion of the bowel will not be considered an adverse event. It will be considered an incidental finding of the subject's disease process. The subject and their 3rd party payor will be responsible for the treatment of these incidental findings.

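### Section 5 clears a child for capsule endoscopy without section 3's condition that the patency capsule pass intact, and states no stop for one still in the small bowel at the 28-40 hour x-ray

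*Combined protocol and SAP*

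**What the plan says.** Section 3 (Study Design) sets the entry condition for WCE: "Those patients, who pass an intact PC, usually within 40 hours, will ingest the wireless capsule endoscopy (WCE". Section 5 (Study Procedures, post patency capsule swallow) is the instruction that staff carry out. It calls for an abdominal x-ray 28 to 40 hours after the swallow, aiming for 30 hours, "unless they report to the study team that they visibly saw the excreted capsule". The go-ahead follows: "If the patency capsule has passed through the bowel then the subject will continue with WCE procedures". A doctor or delegate then discusses the MRE and patency results with the family, and "families will be able to decide if they would like to continue with study procedures".

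Two other places describe what the patency capsule does when it is held up. Section 2 (Background) describes its behaviour as follows: "dissolve starting at 30 hours post ingestion, thus slow passage or retention of PC in the small bowel signals a risk of capsule retention". It adds that this is usually taken as a reason not to give WCE. Section 5 says: "If the capsule is retained more than 80 hours it will dissolve into small pieces that can pass naturally through the GI tract".

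**The concern.** The patency test is informative because a full-size capsule gets through. This capsule is built to leave the bowel even when the test fails, so a rule that asks only whether it has gone does not separate an open bowel from a narrowed one. Intactness, or a clear small bowel early enough, makes that separation. Section 3 states the intactness condition and section 5 does not.

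The stake is safety. Both capsules are given for research. Section 5 accepts that a retained video capsule may need medical treatment and, in some cases, surgery. The other checks before WCE are not fixed stops for a child with narrowing. Section 3 says: "If MRE shows stenosis or stricture subject and caregivers will be given the opportunity to continue with the study or withdraw". For a child who continues on those terms, the patency result is the main protection against retention. The multicentre trial cited in section 2, in which every video capsule passed, is reassuring only for patients in whom the patency capsule had proved patency.

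**Working it through.** No power or sample-size figure bears on this point. The check sets the rules side by side and then does the hour arithmetic on the stated windows.

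**The two rules**

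| Item | Section 3 | Section 5 |
|---|---|---|
| Capsule must be intact | Yes | Not stated |
| Time of passage | Usually within 40 h (not a firm limit) | Not stated in the go-ahead sentence; x-ray at 28-40 h just before it |
| Condition checked when the family reports excretion | Implied by the intactness condition | Not asked; x-ray waived |
| Action if still in the small bowel at the x-ray | Not eligible unless passed intact | None stated; discussion, then family choice |

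No other text in section 5 restores the intactness condition. The exclusion criteria in section 4 cover obstruction, ileus and esophageal stricture, but not small-bowel stricture. Section 8 calls MRE findings that contraindicate WCE screen failures, but says nothing about patency results.

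**Timing inputs**
- X-ray: 28-40 h after the swallow, target 30 h (section 5).
- Dissolving starts: 30 h (section 2).
- Break-up into pieces: retained more than 80 h, with pieces passing after 2-5 days (section 5).
- WCE visit: 5 days plus or minus 2 days after the patency capsule (section 5), so (5 - 2) x 24 = 72 h to (5 + 2) x 24 = 168 h.

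**Route 1: family report.** Dissolving can start at 30 h, before the x-ray window closes at 40 h. A capsule excreted softened between 30 and 40 h, and reported as seen, waives the x-ray and meets the section 5 wording without meeting section 3.

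**Route 2: still present at the x-ray.** The protocol does not say where the 2-5 days start.
- Counted from 80 h: 80 + 48 = 128 h to 80 + 120 = 200 h. The overlap with 72-168 h is 128-168 h, which is after the nominal visit at 5 x 24 = 120 h.
- Counted from the swallow: 48-120 h. Since pieces form only after 80 h, the overlap with 72-168 h is 80-120 h.

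Section 3 also requires WCE within 1 week of MRE. If the patency capsule is swallowed 1 or 2 days after MRE, which section 5 allows, the latest WCE is 168 - 24 = 144 h or 168 - 48 = 120 h after it. On the first count the overlap then shrinks to 128-144 h or disappears. On the second it is unchanged.

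So the stated timings allow a held-up capsule to leave in pieces before WCE, but on one reading only late in the window. These are clock hours. They say nothing about how many children would be affected.

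**The case against.** The strongest reply is that the two sections do not conflict. Section 3 is current text and still binds, and a capsule passed intact has also passed through the bowel, so section 5 can be read as shorthand. The go-ahead sentence directly follows the x-ray instruction, so its natural reading is that passage is judged at about 30 hours. No repeat x-ray is planned. Route 2 would need staff to set aside a film that showed the capsule, against the statement in section 2 about slow passage. A family that says it saw the capsule probably saw something recognisable. A clinician also reviews the results before WCE.

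Much of this stands. A reader might infer that section 5 abolishes the safeguard, or that an x-ray clearance is worthless because a film cannot show what condition the capsule left in. The documents support neither. Section 3 remains in force. Dissolving only starts at 30 hours and break-up is described only beyond 80, so an empty film near 30 hours is good evidence that a near full-size capsule got through.

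Three things are left. The report route waives the film without asking about condition. No stop is written for a capsule still in the small bowel at the x-ray. The clinician's discussion ends in a family choice, and staff are not told to establish intactness before it.

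**Conclusion.** The point holds as an inconsistency between sections 3 and 5 that should be corrected. As written, section 5 lets a child proceed on a report of an excreted capsule whose condition nobody has asked about. It leaves a capsule still in the small bowel at 28-40 hours to discussion and choice, although section 2 treats that result as usually a contraindication.

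Its size cannot be stated as a rate. The documents do not give the share of children who pass a late or non-intact capsule, or the retention risk in such children. The retention figures in section 2 come from other cohorts and do not isolate non-intact passage.

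A reader might also infer that the MRE-WCE comparison is biased. Nothing here shows that: each evaluable child has both examinations, and the point concerns who receives the capsule.

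The conclusion assumes that staff work from section 5, and that the dissolution behaviour is as sections 2 and 5 describe it. It is more than missing detail, because the correction changes who may receive a research-only device.

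**What to change.** Replace the go-ahead sentence in section 5 with:

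> The subject continues to WCE only if the patency capsule was seen excreted intact by the time of the 28-40 hour check, or the 28-40 hour x-ray shows no capsule, fragment or tag in the small bowel. If it is still in the small bowel at that x-ray, or is excreted softened or broken and no x-ray at 28-40 hours shows the small bowel clear, the subject does not have WCE and is recorded as a patency screen failure.

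This keeps the x-ray waiver for a capsule seen intact. It does not hold back a child whose capsule has already reached the colon, and late passage cannot count as clearance. The family discussion can stay for children who meet the rule.

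The cost is a short edit to section 5 and an entry on the data form for capsule condition and time of passage. A few children who would now proceed may become extra screen failures. The documents do not allow that number to be estimated.

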6. DATA COLLECTION

Data Collection Procedures

- The subject's medical record will be reviewed for data collection to include but not limited to, subject demographics, medical and surgical history, imaging results initial disease presentation and patient current clinical status. Data will be collected on a separate paper data collection form.
- The capsule images will be independently interpreted by the PI initially and then confirmed by two gastroenterologists with 4 - 10 years of experience in capsule endoscopy. The results will be reported in the subject's medical record as they would be for standard of care in compliance with the CMH policy on medical record documentation of research subjects. The subjects regular GI provider will review the results of the WCE and consider the results when making decisions about the subjects treatment plan. We will be using the capsule endoscopy data collection form including the Lewis scoring system that is automatically

calculated and included in the RAPID® software. Lewis score is a WCE ranking of inflammatory activity into three levels based on erythema, stenosis, edema and erosions in small intestinal tertiles: 1) no disease or clinically insignificant disease ($LS < 135$); 2) mild disease ($135 \leq LS \leq 790$); and 3) moderate or severe disease ($LS > 790$).

- The study will be considered negative if no abnormalities were seen and as positive if clear abnormalities of the SB mucosa (i.e. ulcerations, erosions, polyps, vascular lesions, and bleeding lesions) were observed. White lesions within a crater with surrounding erythema were considered ulcers, whereas small superficial white lesions, even with surrounding erythema, were considered erosions. If no abnormalities or non-specific findings (such as erythematous spots or mucosal breaks) were seen the examination was considered non-specific or normal.
- The examiners of WCE and MRE will be blinded to each other's findings but will be aware of the patient's history and laboratory data.
- To reduce variation in MRE readings, one radiologist will retrospectively review the MRE for all subjects to provide a consistent assessment of the extent of the subjects' disease.

Records to be kept

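### The plan lets the first capsule reader learn the MRE result before reading, does not reconcile this with its blinding statement, and does not mask the confirming reads

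*Combined protocol and SAP*

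**What the plan says.** Section 5, under the heading on what follows the patency capsule, provides: "The study doctor or the subjects regular GI doctor or an appropriate delegate will discuss the results of MRE and patency capsule". The purpose is to judge retention risk, after which "families will be able to decide if they would like to continue with study procedures". Referring GI providers are to be "listed as study staff when they refer a subject so they are identified as being able to participate in these study procedures".

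Section 3 (Study Design) also acts on the MRE result before WCE: "If MRE shows stenosis or stricture subject and caregivers will be given the opportunity to continue with the study or withdraw". Section 8 (Statistical Considerations) treats subjects with MRE findings that rule out WCE as screen failures. Neither section names the person who takes that step.

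Section 6 describes the reading: "The capsule images will be independently interpreted by the PI initially and then confirmed by two gastroenterologists". It adds: "The examiners of WCE and MRE will be blinded to each other's findings but will be aware of the patient's history and laboratory data". Section 3 labels the study a "Prospective single blinded comparison of a cohort of pediatric patients" and does not say there who is blinded.

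**The concern.** The primary aim is to compare the diagnostic yield of MRE and WCE in the same children. A WCE reading calls for judgement: Section 6 asks the reader to separate clear mucosal abnormalities, such as erosions, from non-specific findings, such as red spots. A reader who already knows the MRE result may lean towards agreeing with it, or may search harder when it is negative.

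The blinding statement is meant to prevent this, but a step written elsewhere in the plan allows the opposite for the first reader, and no procedure protects the statement. If the later readers work from the first reader's result, they may not correct it.

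**Working it through.** The plan gives no figure for this point, so the check is mainly a comparison of the texts.

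**1. Order of events.** The Section 5 discussion settles whether the family continues to WCE. It therefore takes place before the capsule is swallowed, and so before it is read.

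**2. Who may hold the discussion, against who reads.**

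| Person allowed by Section 5 | Reads the capsule under Section 6? | Blinding statement kept? |
|---|---|---|
| Study doctor who is the PI | Yes, first | No, for that subject |
| Study doctor who is not the PI | Not stated | Only if not a reader |
| Regular GI doctor | Not stated; not excluded | Only if not a reader |
| Delegate | Not stated; not excluded | Only if not a reader |

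The alternatives are joined by *or*, so exposure of the PI is possible but not certain. Nothing excludes it.

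**3. Other routes.** The MRE-based choice in Section 3 and the screen-failure decision in Section 8 have no named owner. The chart review in Section 6 takes in imaging results and does not separate the person doing it from the WCE readers.

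**4. The second and third reads.** In Section 6 the word for independence is attached to the PI's reading, and the other two readers confirm. The plan does not say whether they see the PI's result, how a disagreement is settled, or which read is analysed.

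**5. Scale, by illustration only.** Inputs from Section 8 are 34 evaluable subjects, a 23-point target difference and two-sided alpha 0.05 (the value in the sample-size paragraph). One altered WCE call moves the yield difference by 1/34 = 2.9 points.

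To see what systematic shifts could do, take the asymptotic McNemar test. With m discordant subjects, of whom k are WCE-only positive, it rejects when (2k − m)²/m > 3.84. The rejection probability sums over m ~ Binomial(34, p10 + p01) and k given m ~ Binomial(m, p10/(p10 + p01)). Here p10 is the WCE-only positive rate and p01 the MRE-only positive rate. The discordance and shift rates below are assumptions; the documents give none.

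*No true difference (p10 = p01 = q). A fraction f of MRE-only positives is read up to WCE-positive, so p01 becomes q(1 − f) and the apparent WCE advantage is q × f:*

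| q | f = 0 | f = 25% | f = 50% |
|---|---|---|---|
| 10% | 4.6% reject | 6.0% (2.5 points) | 10.6% (5 points) |
| 15% | 4.3% reject | 6.1% (3.7 points) | 13.3% (7.5 points) |
| 20% | 4.5% reject | 6.8% (5 points) | 16.4% (10 points) |

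*True difference of 23 points (p10 = 28%, p01 = 5%):*

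- No shift: difference 28 − 5 = 23 points; power 67.9%.
- Half of WCE-only positives read down to agree with MRE: 14 − 5 = 9 points; power 20.8%.
- Half of MRE-only positives read up instead: 28 − 2.5 = 25.5 points; power 84.9%.

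Reading towards agreement can therefore inflate or shrink the apparent WCE advantage. The 67.9% depends on the assumed discordance and is not a test of the plan's 80% power claim.

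**The case against.** The strongest defence is that both sections can be obeyed together. Section 6 sets a flat rule on blinding and Section 5 offers three alternatives, so a WCE reader can simply leave the discussion to someone else. The study doctor need not be the PI, since Section 5 elsewhere mentions the PI or a sub-investigator. The blinding rule covers WCE examiners in general and so reasonably reaches all three readers. Two experienced readers who do not know the MRE result could be a real check on the first.

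Much of this stands, and it limits the point in three ways:

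- A reader might infer that the blinding is broken or worthless. The documents do not show that: they permit the exposure and do not say how often it would happen, if at all.
- A reader might infer that whatever the PI knows must reach the final result. That does not follow either, because the plan is silent on whether the confirming readers see the PI's read and on which read is analysed.
- A reader might take the illustration as an estimate of bias. It is not one: the shift rates have no source in the documents, and the shifts can run in opposite directions.

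The defence does not remove the gap. A general statement that readers are blinded is not secured while a specific procedure allows the first reader to handle the other test's result. Confirmation that is not stated to be masked cannot be counted as protection.

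**Conclusion.** The point holds as an unreconciled conflict. Section 5 allows the study doctor, who may be the PI, to learn and discuss the MRE result before WCE. Section 6 makes the PI the first WCE reader and says WCE examiners do not know the MRE result. The second and third reads are not an assured safeguard, because they are described as confirmation and no masking is stated.

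This rests on the study doctor being undefined and on no text keeping WCE readers away from MRE results. The size and direction of any bias cannot be estimated from the documents. The change should be made before reading starts, because a reading made with knowledge of the MRE result cannot be re-blinded for that reader.

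**What to change.** **Section 5.** State that the MRE discussion before WCE, and the MRE-based decision on continuing or screen failure, are handled by the regular GI doctor or a delegate who will not read that subject's capsule. Section 5 already allows these people to hold the discussion. Families receive the same discussion, and no clinical rule changes.

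**Section 6.**
- Withhold MRE reports from a subject's WCE readers until that subject's WCE form is locked.
- A reader who already knows the MRE result through routine care does not read that subject.
- The existing readers score separately, masked to each other's reads, before any consensus.
- Prespecify the rule for disagreement and the read used in the analysis: for example, the majority for positive or negative, and a stated rule such as the median for the Lewis score.

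**Cost.** Two fuller scored reads per subject replace two confirmations, and a reader must occasionally step aside. The PI gives up the MRE discussion for subjects whose capsules the PI will read. No new staff are needed for the reading itself, although recusals may need cover from within the existing group.
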